5.1 Overall design (including assumptions, type, etc.)

This study hypothesized selmetinib hydrosulphate capsules for neurofibromatosis type I, including improving the resectable range of surgery, shrinkage, delaying progression, reducing recurrence, and improving function. A prospective, single-arm, phase study design is

estimated to improve the resectable range of NF 1 surgery, with objective response rate (ORR) in 40%, duration (DOR) in more than 30% of patients, and progression-free survival (PFS) in more than 12 months in 90% of patients.

5.2 Study design process

5.2.1 Study the specific implementation process

This study started from the recruitment of subjects, with clinical diagnosis, definite diagnosis by pathological biopsy, primary screening according to inclusion criteria, and exclusion criteria, and enrollment after signed informed consent. Patients evaluated as no indication for surgical resection and treated with selmetinib hydrosulphate capsules. Based on individualized patient body surface area (BSA), oral selmetinib hydrosulphate capsules daily (20–50mg bid) were evaluated for shrinkage efficacy, ORR and surgical resection after 6 cycles.

vital sign	✓	✓	✓	✓	✓	✓	✓	✓	✓
electrocardiogram	✓				✓			✓	✓
routine blood test	✓		✓	✓	✓	✓	✓	✓	✓
Blood biochemical	✓		✓	✓	✓	✓	✓	✓	✓
Liver, kidney, and heart function	✓		✓	✓	✓	✓	✓	✓	✓
coagulation function	✓		✓	✓	✓	✓	✓	✓	✓
Heart ultrasound	✓				✓			✓	✓
Pathological biopsy	✓								
Infectious disease examination (hepatitis B, hepatitis C, HIV, syphilis)	✓								
Imaging examination	✓				✓			✓	✓
complication And adverse event assessment			✓	✓	✓	✓	✓	✓	✓

5.3 Methods to reduce bias (e. g., randomization, blindness, matching method, etc.)

The end of this study was defined as the last subject who completed the last follow-up or was lost to follow-up or died

5.4 Definition of end of study (e. g. last subject completes last follow-up)

5.5 Statistical analysis

5.5.1 Sample size and calculation basis

The estimated sample size was based on the objective response rate. The study hypothesis is that selmetinib sulphate capsule has shrinkage effect on NF 1. The study parameters are set: $\alpha = 0.025$ (one side),

Power=90%. Based on the results of relevant study or pre-test, the objective response rate (ORR) is expected to reach 40%, 29 cases were calculated using PASS 15.0 software, and considering 10% shedding rate, 33 subjects should be included.

5.5. 2 Data analysis set (e. g. full analysis set, compliance protocol set, safety analysis set)

Statistical analysis will be performed using the SAS statistical software (V. 9.4, SAS Institute) Statistical analysis software for calculation, if no special instructions, the main indicators use one-sided test, control the first class error α is 0.025, the remaining indicators use two-sided test, one class error is $\alpha = 0.05$. To calculate confidence intervals, calculate two-sided 95% confidence intervals if not otherwise specified.

(1) Full analysis set (full analysis set, FAS): consisting of all subjects who received at least one drug / treatment and obtained efficacy assessment. This dataset was derived from all subjects after removing subjects in the least and reasonable way.

(2) Safety analysis set (safety analysis set, SS): a population treated at least once / once and having at least one safety evaluation data. In the safety analysis, all patients will be analyzed by the actual drug drug group.

(3) Compliance with the protocol set (per-protocol set, PPS): all concomitant medications that met the trial protocol and did not use the impact effectiveness evaluation, good medication compliance (between 80% and 120%), excluded subjects who had major protocol violations and were judged to have a significant impact on the results. All protocol deviations excluding subjects from the compliant protocol set will be described in detail in the Statistical Analysis Plan (SAP) and completed prior to data lock.

5.3 5 Statistical analysis plan

Data description of statistical analysis, analysis method of primary / secondary indicators / safety indicators, statistical school positive method, control of bias, stratification / subgroup / sensitivity analysis, etc

Demographic, and other baseline characteristics

Based on the analysis of FAS set, the demographic data, medical history, vital signs and other baseline data were statistically described, where the measurement data (age, BMI, XX, etc.) gave mean, SD, minimum, maximum, median, and gave frequency and corresponding percentage for count data (gender, XXX, etc.).

Analysis of efficacy indicators

(1) Main efficacy indicators

Point estimates for the main evaluation index (ORR) and estimated two-sided 95% confidence intervals using the Clopper–Pearson exact probability method. If the lower limit of the 97.5% confidence interval was less than the ORR rate of the historical control, the efficacy was considered better than the historical control.

(2) Secondary efficacy indicators: analysis using FAS and PPS analysis sets. For survival metrics, the digit survival time and its two-sided 95% confidence intervals were calculated. For the rate of each index, point estimates were performed and two-sided 95% confidence intervals were estimated using the Clopper–Pearson exact probability method. For the continuity index, the mean and two-sided 95% confidence intervals were calculated based on the normal distribution method, otherwise the median and two-sided 95% confidence intervals were calculated based on the percentile method.

Safety index analysis

The SS set was used to provide a statistical description of the incidence of adverse events / serious adverse events and adverse reactions, and to list the details of the occurrence of each adverse event in each subject, including the type and severity of adverse events. Evaluation of laboratory indicators, vital signs, electrocardiogram and other safety related indicators, compare and evaluate the changes before and after treatment, and give a statistical description of the clinical evaluation (normal, abnormal without clinical significance, abnormal with clinical significance, not checked) before and after treatment.

Principles of handling missing / deletion / follow-up data

LOCF (last observation carried forward), that is, the main index data is not observed at the last time; the secondary indicators and safety indicators are not filled.

6. Research intervention*

6.1 Study intervention content (description of intervention content, implementation steps, dose and route of intervention drug, frequency of intervention, product of test group and control group, etc.)

All patients received oral selmetinib hydrosulphate capsules (20–50mg bid) daily for 30 days for 6 cycles on patient body surface area (BSA).

6.2 Preparation / handling / storage / responsibilities (allocation plan for the drug and control article when the intervention is drug)

Use of a medication must be recorded in the patient's medical record and in the appropriate location of the CRF. After the enrollment of the subjects and at the 1st and 2nd months of follow-up, the executive nurse shall receive the corresponding number of drugs at the drug administrator, and the remaining drugs and packaging boxes shall be returned to the drug

administrator. If the drug is found or damaged during the preparation process, this box of drugs should not be used, the damaged drugs shall be treated as empty bottles, and other undamaged drugs shall be returned to the drug administrator together with the packaging box. The study center shall be responsible for the management of test drugs, including receiving, distribution, counting and recovery. The investigator shall ensure that the test drug is stored in a safe, independent and locked place at the study site and that the storage conditions shall meet the storage requirements of the test drug. No one can be contacted without the consent of the investigator. Empty boxes shall be stored and managed as the test drug.

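### The historical-control response rate that defines primary success, and that n=29 was computed against, is stated nowhere in the protocol

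*Protocol*

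**What the plan says.** Protocol section 5.5.1 gives the inputs "The study parameters are set: $\alpha = 0.025$ (one side") and 90% power. The expected rate is introduced with "Based on the results of relevant study or pre-test", and no study is identified. The section continues: "the objective response rate (ORR) is expected to reach 40%, 29 cases were calculated using PASS 15.0 software", and then, "considering 10% shedding rate, 33 subjects should be included". The hypothesis in that section is only that the drug shrinks the tumour; it contains no null value. The software is named, but not the test or procedure.

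Section 5.1 repeats the expected rate ("with objective response rate (ORR) in 40"%) and gives no comparator.

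Under the main efficacy indicators in section 5.5, ORR is to be estimated with a two-sided 95% Clopper–Pearson interval. The efficacy conclusion then depends on a comparison that begins "If the lower limit of the 97.5% confidence interval was less than the ORR rate of the historical control". Neither the value of that historical rate nor its source appears there or anywhere else in the protocol, including the abstract and sections 3.1 and 3.2. Nothing at these places suggests redacted or lost text.

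**The concern.** A single-arm trial has no concurrent comparator, so the historical rate does all the comparative work. It is an input to the sample size and it is the threshold of the primary decision. With the value missing, three things fail:

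- the primary rule cannot be applied to a given number of responders;
- neither the 0.025 type I error nor the 90% power can be verified;
- nothing in this document fixes the threshold before responses are seen.

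A protocol does not commonly leave this to the statistical analysis plan. The number had to exist when 29 was calculated, and the protocol reports both the calculation and the rule that depends on it.

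**Working it through.** **Inputs from the protocol (5.5.1 and the main efficacy indicators).** One-sided alpha 0.025 (z = 1.960), power 90% (z = 1.2816), alternative p1 = 0.40, n = 29, dropout 10%, Clopper–Pearson interval. The null p0 is not given, so every p0 below is an assumption.

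**Reading of the success rule.** The text mentions a 97.5% interval and says the lower limit must be less than the historical rate. I take it to mean that the lower limit of the two-sided 95% (one-sided 97.5%) Clopper–Pearson interval must exceed p0. This fits the stated one-sided 0.025 and is equivalent to the exact binomial test.

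**Step 1: the plan's own figures.** The dropout step reproduces: 29/0.9 = 32.2, rounded up to 33. The 29 cannot be reproduced from the stated inputs, because p0 is missing.

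**Step 2: which null would give 29?** Solving backwards on a 0.001 grid, with some common formulas (not a complete list):

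| Formula | Check | p0 giving n = 29 |
|---|---|---|
| Alternative variance only: (1.960+1.2816)²·0.24/(0.40−p0)² | 28.02 at 0.10 | 10.0–10.5% |
| Arcsine: [(1.960+1.2816)/(2·asin√0.40 − 2·asin√p0)]² | 28.95 at 0.14 | 13.7–14.0% |
| z-test with continuity correction | – | 13.7–13.9% |
| z-test: [(1.960·√(p0(1−p0)) + 1.2816·√0.24)/(0.40−p0)]² | 28.20 at 0.15; 16.4 at 0.10 | 15.0–15.2% |
| Null variance only: (1.960+1.2816)²·p0(1−p0)/(0.40−p0)² | 28.03 at 0.17 | 17.0–17.2% |
| Exact binomial, smallest n with power ≥ 90% | 27 for p0 0.127–0.137; 30 for 0.138–0.147 | none from 2% to 25% |

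The last row suggests that a normal approximation was used. It does not show an error.

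**Step 3: what each null implies under the exact rule.** The pass mark is the smallest x with P(X ≥ x | n, p0) ≤ 0.025. Power is P(X ≥ x | n, 0.40).

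| Assumed p0 | n = 29: pass mark, alpha, power | n = 33: pass mark, alpha, power |
|---|---|---|
| 10% | 7, 2.2%, 97.7% | 8, 1.4%, 98.1% |
| 15% | 9, 2.2%, 88.1% | 10, 1.9%, 90.8% |
| 17% | 10, 1.8%, 78.5% | 11, 1.7%, 83.1% |

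A 14% null has the same pass marks and power as 15% (9 of 29, 10 of 33).

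**Step 4: how high can the null be with 90% power kept?** At n = 29 the largest pass mark that keeps 90% power is 8 responders (94.3%). The lower limit for 8/29 is 12.7%. At n = 33 it is 10 responders (90.8%), and the lower limit for 10/33 is 15.6%. So 90% power holds for nulls up to 12.7% with 29 analysed, and up to 15.6% with all 33.

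**Step 5: how often would the verdict depend on the missing number?** At a true ORR of 40%:

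- 10% against 15%: the verdict differs at 7–8 of 29, probability 9.5%; at 8–9 of 33, 7.4%.
- 10% against 17%: it differs at 7–9 of 29, probability 19.1%.

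**Step 6: sensitivity to the reading.** If a two-sided 97.5% interval were intended, the pass marks at n = 29 would be 8 for a 10% null (power 94.3%) and 10 for a 15% null (78.5%).

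**The case against.** The best defence is that 29 is a plausible number. The ordinary z-test returns it at a round null of 15%, and exact power is then 88.1% at 29 and 90.8% at 33, within about two points of target. A completed software result also implies that some null was entered before enrolment, and an unseen analysis plan may record it. On this view the text shows non-reporting, not a threshold left open. The wider spread, especially 78.5% and 19.1%, rests on a 17% null from a simplified formula.

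Much of this stands. The sample size should not be called wrong, 15% is a reasonable guess, and 17% is best treated as an outer bound. All the discordance probabilities also assume a true ORR of exactly 40%. But a guess at the null does not make the primary rule executable. The only matter that section 5.5 expressly leaves to the analysis plan is the protocol deviations that exclude subjects from the per-protocol set; it does not defer the historical rate. The defence does not supply the missing number.

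**Conclusion.** The point holds and must be fixed. The protocol's primary success rule has no threshold, and its 90% power claim cannot be checked. Over the nulls that return 29 under the formulas tried, the pass mark runs from 7 to 10 of 29 and exact power from 97.7% to 78.5%. At the most natural candidate, 15%, they are 9 of 29 and 88.1%. These figures rest on assumed nulls, a true ORR of 40%, and the reading of the success rule given above. They measure how much depends on the missing figure; they do not show that the trial is underpowered.

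**What to change.** In section 5.5.1, state the null ORR that was entered, its source and the test procedure used. Put the same number into the rule under the main efficacy indicators: success if the lower limit of the two-sided 95% (one-sided 97.5%) Clopper–Pearson interval for ORR exceeds that null. This wording also corrects the direction of the comparison and the interval level. Keep the lower-limit rule as the operative one, since the number analysed may be neither 29 nor 33. Add the minimum responder count, exact alpha and exact power at both sizes.

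For illustration only, if the null was 15%: at least 9/29 (alpha 2.2%, power 88.1%) or at least 10/33 (alpha 1.9%, power 90.8%).

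The cost is protocol wording and one recalculation. The restated power may fall below 90%: 88.1% at 29 for a 15% null, and 78.5% at 29 or 83.1% at 33 for a 17% null. Reporting the true figure is enough to close this point and needs no extra patients. If the sponsor wishes to hold 90% by exact calculation, the smallest n is 33 analysed at a 15% null and 39 at 17%.

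### The primary success rule is inverted: it declares efficacy when the lower confidence limit falls below the historical ORR

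*Protocol*

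**What the plan says.** The protocol describes a single-arm trial whose primary endpoint, ORR, is judged against a historical rate.

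- **Section 5.5.2** sets the error rate for the primary analysis: "the main indicators use one-sided test, control the first class error α is 0.025".
- **Section 5.5.1** sizes the trial with one-sided α = 0.025, 90% power and an expected ORR of 40%: "29 cases were calculated using PASS 15.0 software", and then "considering 10% shedding rate, 33 subjects should be included".
- **Statistical analysis plan section, Main efficacy indicators**, first calls for "Point estimates for the main evaluation index (ORR) and estimated two-sided 95% confidence intervals" by the Clopper–Pearson method. It then gives the decision rule: "If the lower limit of the 97.5% confidence interval was less than the ORR rate of the historical control, the efficacy was considered better".

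No other section states a success rule for the primary endpoint, and no section gives a value for "the ORR rate of the historical control".

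**The concern.** A lower limit below the benchmark means that the data are still compatible with a response rate no better than the benchmark. That is the result in which superiority has not been shown, yet the protocol attaches the claim of superiority to it. Taken literally, the rule rewards a lack of response, and the stated one-sided 2.5% error and 90% power cannot hold. The trial's main conclusion rests on this sentence.

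There is a smaller problem in the same place. The interval to be computed is two-sided 95%, but the rule refers to a 97.5% interval without saying whether it is one- or two-sided. Only the one-sided 97.5% bound, which is the lower limit of the two-sided 95% interval, matches α = 0.025. A two-sided 97.5% interval would test at 0.0125.

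**Working it through.** **Inputs from the protocol.** One-sided α = 0.025, power 90%, expected ORR p1 = 0.40, n = 29 before dropout and 33 enrolled (section 5.5.1); Clopper–Pearson interval (Main efficacy indicators). **Assumed:** the historical ORR p0, which the protocol does not give. It is varied from 5% to 30%.

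**1. The protocol's own sample size.** Without p0, 29 cannot be reproduced directly, but it can be solved backwards.

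- Normal approximation with null variance, p0 = 0.15: n = [(1.960·√(0.15·0.85) + 1.282·√(0.40·0.60)) / 0.25]² = 28.2, rounded up to 29.
- Normal approximation with alternative variance, p0 = 0.10: n = (1.960 + 1.282)²·0.24 / 0.30² = 28.0; unrounded it is just above 28, so it rounds up to 29.
- Exact binomial: 27 at p0 = 13% and 30 at p0 = 14%; no p0 on the grid examined gives exactly 29.
- Dropout: 29 / 0.9 = 32.2, rounded up to 33, which agrees with the protocol.

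The stated size therefore points to a historical ORR of roughly 10% to 15%.

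**2. The direction of the rule, without any p0.** For x responders out of n, the Clopper–Pearson lower limit is L(x) = the 0.025 quantile of Beta(x, n − x + 1), with L(0) = 0. L(x) rises with x. A rule of the form L(x) < p0 therefore passes every count up to some cut-off and fails every count above it. At x = 0 it passes for any p0 > 0; at 29/29, L = 0.881 and it fails for any p0 in the range considered.

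**3. Size at n = 29.** At p0 = 15%, L(8) = 0.127 and L(9) = 0.153, so the written rule passes 0 to 8 responders and fails 9 or more. The probability of passing is P(X ≤ c) with X ~ Binomial(29, p), where c is the largest count with L(c) < p0. The reversed rule passes at X ≥ c + 1.

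| Assumed p0 | Written rule passes at | P(pass), true ORR = p0 | P(pass), true ORR = 40% | Reversed rule passes at | Type I error | Power at 40% |
|---|---|---|---|---|---|---|
| 5% | ≤ 4 | 98.6% | 0.2% | ≥ 5 | 1.4% | 99.8% |
| 10% | ≤ 6 | 97.8% | 2.3% | ≥ 7 | 2.2% | 97.7% |
| 15% | ≤ 8 | 97.8% | 11.9% | ≥ 9 | 2.2% | 88.1% |
| 20% | ≤ 10 | 98.0% | 34.3% | ≥ 11 | 2.0% | 65.7% |
| 25% | ≤ 12 | 98.4% | 63.7% | ≥ 13 | 1.6% | 36.3% |
| 30% | ≤ 14 | 98.8% | 86.4% | ≥ 15 | 1.2% | 13.6% |

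If the true ORR is close to zero, the written rule passes with probability close to 100%.

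**4. Size at n = 33.** Over the same p0 values, the written rule passes with probability 97.7% to 98.6% when the true ORR equals p0. At a true ORR of 40% it passes with probability 0.05%, 1.9%, 9.2%, 27.6%, 54.7% and 79.4%. With the inequality reversed and p0 = 15%, success needs at least 10 of 33, with type I error 1.95% and power 90.8%.

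**5. The interval label.** With the inequality reversed, n = 29 and p0 = 15%, the two-sided 95% lower limit requires 9 responders (power 88.1%). Reading 97.5% as two-sided requires 10 (type I error 0.74%, power 78.5%).

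**The case against.** The strongest reply is that this is a slip of wording. The English reads as a rough translation throughout, comparison signs have dropped out of several laboratory thresholds in the inclusion criteria, and a lost negation is easy to imagine. The intent can be recovered from the one-sided test at 0.025, the 90% power and the sentence's own conclusion, so a trial statistician would be unlikely to apply the rule literally. This is a fair account of how the error probably arose, and it argues against reading it as a flawed design. It does not put a correct rule on record: section 5.5.2 gives the error rate but not the direction of the test, and changing the inequality once results are known would be a post-hoc change to the primary criterion.

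Two further points are right but do not alter the conclusion. First, whether an effective drug usually fails depends on p0. At a true ORR of 40% the written rule fails it more often than not only for p0 up to about 23.5% (n = 29) or 22.9% (n = 33). Above that the trial is underpowered, so even a drug with a 40% ORR often has a lower limit below p0. Second, the 97.5% label has a natural reading, the one-sided bound, which agrees with section 5.5.2. It needs clarifying but adds little to the seriousness.

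**Conclusion.** The concern holds. The protocol's only explicit primary success rule is the reverse of superiority and contradicts its own one-sided α of 0.025 and 90% power. The direction error depends on no outside figure.

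Its size depends on an assumed historical ORR. At every value from 5% to 30%, a drug no better than the historical rate is declared better with probability of about 98% or more (n = 29), against an intended maximum of 2.5%. At the 10% to 15% implied by the sample size, a drug with the planned 40% ORR would be failed about 98% to 88% of the time. Reversing the inequality restores type I error below 2.5% at every value examined. This must be corrected before any efficacy analysis.

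**What to change.** Replace the decision sentence under Main efficacy indicators with wording to this effect:

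> Efficacy is concluded to be better than the historical control if the lower limit of the two-sided 95% Clopper–Pearson interval for ORR (equivalently, the one-sided 97.5% lower bound) is greater than the historical-control ORR.

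Use that one interval throughout. State the historical ORR as a number with its source, both here and in section 5.5.1; without it the corrected rule still cannot be applied. Any separate statistical analysis plan should carry the same sentence.

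The cost is one sentence and one figure. Visits, assessments and drug supply are unaffected. Section 10 requires ethics committee approval of a revised protocol before it is implemented.

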6.3 Study Intervention Compliance (How to maintain, evaluate, and verify study compliance)

After each medication, the subject should be required to return to the study center for review, and the compliance of the study can be verified according to the subject's review. During the late follow-up, the study team members must conduct a telephone follow-up communication with the subject and reasonably arrange the review visit.

6.4 Concomitant therapy (permitted adjuvant medication, complementary / replacement therapy)

If the subject has hypertension, diabetes, coronary heart disease and other diseases that need long-term drug control, the investigator and the relevant specialist should evaluate the impact of the disease and the relevant study protocol and determine the dose and duration of adjuvant medication.

6.4.1 Rescue (drug, treatment methods, relevant records.....)

The life hazards during the implementation of the clinical study protocol should be implemented in accordance with the clinical rescue plan, such as cardiopulmonary resuscitation, emergency airway management,

emergency surgical treatment, relevant records during hospitalization should be recorded in the medical record system, after discharge should be recorded in the adverse event record form, and the investigator should analyze whether the rescue causes are related to the study and discuss and discuss synchronously in the rescue records.

7. Discontinuation of the study intervention / subject discontinuation and withdrawal*

7.1 Study Intervention discontinuation (reasons / criteria: such as how many adverse events occurred, length of study discontinuation, how data were collected during discontinuation and how to reactivate the study intervention, whether follow-up was continued during discontinuation)

If the Grade 5 adverse event of CTCAE 5.0 standard reaches 10% of the number of subjects, the study should be discontinued, and the drug safety of the study protocol should be discussed to determine whether to adjust the dose of drugs in the study protocol, continue the follow-up during the study suspension, and maintain the follow-up record of the original subject.

7.2 Subjects discontinuation / withdrawal from the study (possible reason for subject discontinuation; involving implantable device, discuss how to remove / replace, obtain alternative materials, later contact with the subject, etc.)

When the subject stops or withdraws from the study due to dissatisfaction with the treatment effect of the study plan or his own economic reasons, he should actively communicate with the subject, encourage the subject to actively treat and help them apply for public welfare funds to complete the treatment. If the subject clearly withdraws, the investigator can continue to complete the follow-up without the study intervention.

7.3 Loss to follow-up (measures to reduce and reduce missing data due to loss to follow-up)

The investigator should keep the contact information of multiple subjects and the contact information of the family members after the subjects are enrolled. The investigator should actively contact the subjects by phone after leaving the hospital, timely understand the condition and arrange the subject to the hospital in advance for the next stage of treatment.

8. Adverse events and unexpected events

Adverse events (AEs) are adverse medical events occurring after the subject receives treatment, but they are not necessarily causally related to the treatment. An adverse event can be any adverse and unexpected signs (including abnormal laboratory findings), symptoms, or illness associated to the use of treatment, regardless of relation to treatment.

It includes, but is not limited to, :

- (1) the exacerbation of the preexisting disease before the use of the study treatment measures;
- (2) The frequency or severity of existing episodes before the use of study treatment;
- (3) Abnormal changes detected or diagnosed after the use of the study treatment measures, although such abnormal changes may have existed before the treatment;
- (4) deterioration of disease or symptoms that persisted before the study.

Causal relationship between adverse events and treatment measures:

In the trial, the investigator should make a comprehensive analysis according to the specific situation of adverse events and the past history, concomitant diseases and concomitant medication to judge the relationship between adverse events and treatment measures. The relationship between

adverse events and treatment measures is divided as "definitely related, most likely related, likely related, possibly unrelated and unrelated".

None: Adverse events were not associated with treatment measures.

Probably unrelated: The occurrence of adverse events is more likely related to other factors such as medication or concomitant

Disease, or the timing of the event suggests that it is unlikely to be causally related to treatment measures.

Possible concern: Adverse events may be caused by therapeutic measures. Cannot exclude whether it may be caused by other

Factors, such as: medication conditions or concomitant diseases. The occurrence of adverse events and treatment measures have a reasonable time order, and the causal relationship between events and treatment measures cannot be excluded.

It is likely that: adverse events may be caused by treatment measures. There is a reasonable temporal sequence of event occurrence and treatment measures.

Positive concern: The type of adverse event has been identified as treatment and no other reason

Explanation, such as: medication status and concomitant diseases. The timing of the event strongly suggests causality.

The adverse event severity criteria can be according to the CTCAE 5.0 (US Department of Health and Human Services). Beyond the above criteria list, refer to the following criteria:

Mild: Symptoms or signs but tolerable.

Moderate; discomfort enough to interfere with normal life.

Severe: Normal activities are already impossible.

All information about adverse events, whether mentioned by the patient, found by the investigator, or found by physical examination, laboratory examination, etc., should be recorded on the study medical

record and case report form. During the trial, the time, duration, symptoms, signs, severity, measures taken, outcome and relationship assessment of adverse events should be carefully observed and recorded, and the trial should be appropriately followed up.

Possible adverse events include: medication-related complications; procedure-related complications; and related complications after withdrawal.

The investigator should use medical terms / concepts to record AEs or SAEs. Its type, degree, occurrence time, duration, treatment measures, treatment are recorded in detail. The association of the combination of complications and medication with the study treatment was evaluated. All AEs (including SAEs) should be recorded on the Adverse Event Form for the CRF. Any patient who is treated must be evaluated for toxicity. The occurrence of any adverse events (AEs) should be graded according to the NCI Common AE classification criteria (NCI-CTCAE version 5.0).

9. Data collection and management

